7. MEASUREMENT OF EFFECT

7.1 Antitumor Effect

Participants will be evaluated for CA-125 response every 4 weeks.

7.1.1 Definitions

Response will be defined according to GCIG criteria which requires a reduction of CA-125 of \geq 50% relative to pre-treatment CA-125 level, maintained for at least 28 days [54].

CA-125	Non-target lesions	New lesions	Overall serological response
Response and	CR	No	CR
normalized			
Response	Non-PD	No	PR
Normalized but not	Non-CR/Non-PD	No	SD
response			
PD	Any	Yes or No	PD
Any	PD	Yes or No	PD
Any	Any	Yes	PD

7.2 Other Response Parameters

Doubling time of CA-125 in the 3 months prior to enrollment compared to doubling time following enrollment.

Progression, defined as development of clinical symptoms deemed secondary to ovarian cancer and/or radiographically visible disease and/or a doubling in the pre-treatment CA-125 value, confirmed on successive measurements (1-3 weeks after initial measurement).[54] Zafirlukast should be continued until progression is confirmed.

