Monitoring for recurrence of ovarian cancer following initial therapy includes serial measurement of the tumor marker CA-125. Tumor marker-only relapse is defined as the absence of recurrent disease by imaging or symptoms along with a rising CA-125, i.e. CA-125 more than twice the upper limit of normal (35 U/mL) in the setting of a normal baseline CA-125 levels or CA-125 greater than twice the nadir count on two successive measurements for CA-125 values that remain above baseline. A randomized study evaluated the benefit of early versus delayed chemotherapy in patients with tumor marker-only relapse of ovarian cancer [11]. Early treatment was started within 28 days of CA-125 increase while delayed treatment was started in response to clinical or symptomatic relapse. There was no difference in overall survival between the arms. In light of these results, observation is currently standard-of-care for tumor marker-only relapsed ovarian cancer. For patients desiring systemic treatment, endocrine therapy is typically preferred given reduced toxicity compared to cytotoxic chemotherapy. This approach has been observed to result in a 17% response rate in CA-125 per GCIG criteria in patients with estrogen receptor-positive ovarian cancer [12]. However, it has not been shown to improve progression-free or overall survival compared to observation in this population.

Venous Thromboembolism and Ovarian Cancer

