3.1 Eligibility Criteria

- 3.1.1 Participants must have histologically confirmed epithelial ovarian, fallopian tube, or primary peritoneal cancer.
- 3.1.2 Participants must have completed at least first-line platinum based chemotherapy and surgery with a response, in the opinion of the investigator, defined as no evidence of disease progression or rising CA-125 at any time during front-line treatment.
- 3.1.3 Participants must meet criteria for tumor marker-only relapse, defined as CA-125 more than twice the upper limit of normal (35 U/mL) in the setting of a normal baseline CA-125 levels or CA-125 greater than twice the nadir count on two successive measurements for CA-125 values that remain above baseline without measurable radiographic disease.
- 3.1.4 Minimum age ≥ 18 years. Because no dosing or adverse event data are currently available on the use of zafirlukast in participants under 18 years of age with ovarian cancer, children are excluded from this study but will be eligible for future pediatric trials.
- 3.1.5 Life expectancy of greater than 4 months.
- 3.1.6 ECOG performance status ≤ 2 (Karnofsky $\geq 60\%$, see Appendix A).
- 3.1.7 Participants must be able to swallow tablets.
- 3.1.8 Participants must have adequate organ and marrow function as defined below:
 - Absolute neutrophil count ≥1,000/mcL

Version Date: 12/21/22

- Platelets >90.000/mcL

- Total bilirubin $\leq 1.3 \times \text{institutional upper limit of normal (ULN)}$

AST(SGOT)/ALT(SGPT)
 Creatinine
 ≤ 2 × institutional ULN
 ≤ institutional ULN

OR

- Glomerular filtration rate (GFR) \geq 45 mL/min/1.73 m²

- 3.1.9 The effects of zafirlukast on the developing human fetus are incompletely characterized. For this reason, women of child-bearing potential must agree to use adequate contraception (hormonal or barrier method of birth control; abstinence) prior to study entry and for the duration of study participation. Should a woman become pregnant or suspect she is pregnant while she or her partner is participating in this study, she should inform her treating physician immediately. Men are not eligible for this study.
- 3.1.10 Ability to understand and the willingness to sign a written informed consent document.

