1.5 Criteria for Taking a Participant Off Protocol Therapy

Duration of therapy will be ongoing (+/- 7 days inclusion of windows) for up to 12 cycles or until one of the following criteria apply:

- Intercurrent illness that prevents further administration of treatment
- Unacceptable adverse event(s)
- Participant demonstrates an inability or unwillingness to comply with the oral medication regimen and/or documentation requirements
- Participant decides to withdraw from the study, or general or specific changes in the
 participant's condition render the participant unacceptable for further treatment in the
 opinion of the treating investigator
- Clinical or radiographic progression of ovarian cancer
- Doubling the pre-treatment CA-125 value (confirmed at least 1 week apart)
- Grade 3 or 4 hemorrhage and/or symptomatic bleeding in a critical area or organ such as intracranial, intraspinal, intraocular, retroperitoneal, intra-articular or pericardial, or intramuscular with compartment syndrome, and/or bleeding causing a fall in hemoglobin level > 2 g/dL or bleeding leading to a transfusion of > 2 units of packed red blood cells

Version Date: 12/21/22

Participants will be removed from the protocol therapy when any of the criteria listed above applies. The reason for removal from protocol therapy, and the date the participant was removed, must be documented in the study-specific case report form (CRF). Alternative care options will be discussed with the participant.

In the event of unusual or life-threatening complications, participating investigators must immediately notify the Principal Investigator, [name] at [contact].

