9.2 Sample Size, Accrual Rate and Study Duration

Version Date: 12/21/22

In the 4 women treated with zafirlukast 40 mg twice daily, there were no responses in terms of decline of CA-125. However, However, the mean change in CA-125 was 0.036 U/mL per day prior to treatment compared with 0.015 U/mL per day following zafirlukast (paired t-test p=0.026). This equated to a mean CA-125 doubling time of 29.8 days in the weeks prior to treatment compared with a mean doubling time of 85.69 days following treatment.

A second cohort of 4 women at 80 mg twice daily will be enrolled to assess whether CA-125 doubling time is significantly prolonged compared with pre-treatment values and whether we observe PDI inhibitory activity in plasma using Di-eosin-GSSG assay.

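### CA-125 progression in 7.2 is anchored to the pre-treatment value, so a woman with a CA-125 response must rise at least fourfold from her nadir before a CA-125-based PFS event is counted (minor)

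*Combined protocol and SAP*

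**What the plan says.** The only definition of progression written out in the protocol is in 7.2 (Other Response Parameters): symptoms attributed to ovarian cancer, disease visible on imaging, "and/or a doubling in the pre-treatment CA-125 value, confirmed on successive measurements", with the confirming CA-125 taken 1 to 3 weeks later. The off-therapy criteria in 1.5 use the same anchor: "Doubling the pre-treatment CA-125 value (confirmed at least 1 week apart". Section 7.2 also ties continuation of zafirlukast to confirmed progression.

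Response in 7.1.1 is a reduction of at least "50% relative to pre-treatment CA-125 level, maintained for at least 28 days". The table there has a PD entry in its CA-125 column but does not define it.

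Marker relapse at entry (2.1 and 3.1.3) is defined in two limbs. After normal values it is "CA-125 more than twice the upper limit of normal (35 U/mL) in the setting of a normal baseline CA-125 levels", that is, above 70 U/mL. Otherwise it is "CA-125 greater than twice the nadir count on two successive measurements for CA-125 values that remain above baseline".

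PFS is an exploratory objective (1.3). Section 9.5 lists it with no event definition and no analysis method, so 7.2 has to supply the event.

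**The concern.** The entry rule measures relapse from the lowest value reached, or from the normal range. The on-study CA-125 rule measures progression from the pre-treatment value and disregards any later nadir. The two agree for a woman whose CA-125 never falls and diverge as soon as it does.

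Suppose a woman enters at 200 U/mL, falls to 30 and climbs back to 80. If confirmed, 80 exceeds 70 and meets the marker limb of the protocol's relapse definition. It is also still 60% below 200 (120/200), so it meets the size of reduction required for response. Under 7.2 her CA-125 does not count as progression until 400.

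What is at stake is how PFS is read. Where CA-125 is the first route to progression, the definition lengthens PFS only in women whose marker falls, and always in the same direction.

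**Working it through.** The documents state no figure for this point, so there is none to reproduce. The check is direct arithmetic.

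**Inputs.** Let B be the pre-treatment CA-125 and r the fractional fall to nadir.
- Progression threshold: 2B (7.2)
- Response: r of at least 0.5 (7.1.1)
- Relapse threshold: 70 U/mL after normalisation, otherwise twice the nadir (3.1.3)
- Mean doubling times: 29.8 days before treatment and 85.69 days on 40 mg twice daily (9.2)
- CA-125 evaluated every 4 weeks (7.1)

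**Assumption.** After nadir, CA-125 rises exponentially at one of the two mean doubling times.

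**Step 1: rise needed from nadir.** The nadir is B(1 − r), so the fold rise to reach 2B is 2B / [B(1 − r)] = 2/(1 − r). Under a twice-nadir rule it is always 2. The delay is log2[1/(1 − r)] doublings. For a woman whose CA-125 does not normalise:

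| Fall r | Fold rise to 2B | Delay, doublings | Days at 29.8 | Days at 85.69 |
|---|---|---|---|---|
| 0% | 2.0 | 0 | 0 | 0 |
| 25% | 2.7 | 0.42 | 12.4 | 35.6 |
| 50% | 4.0 | 1.00 | 29.8 | 85.7 |
| 75% | 8.0 | 2.00 | 59.6 | 171.4 |
| 90% | 20.0 | 3.32 | 99.0 | 284.7 |

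**Step 2: women who normalise.** The relapse threshold is 70, so the delay is log2(2B/70) doublings.
- B = 100: log2(200/70) = 1.51 doublings, 45.1 to 129.8 days.
- B = 200: log2(400/70) = 2.51 doublings, 74.9 to 215.5 days.

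**Step 3: the minimum for any responder.** If the second limb of 3.1.3 is read as covering women whose CA-125 stayed above 35, entry by either limb implies B > 70.
- A responder who normalises has 2B/70 > 2.
- One who does not has a nadir of at most B/2, so twice her nadir is at most B, and 2B/B = 2.

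In both cases the 3.1.3 rule is met at least one doubling time earlier: 29.8 to 85.7 days or more.

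**Step 4: the example (200, nadir 30).** At 29.8 days she crosses 70 at 29.8 × log2(70/30) = 36.4 days after nadir and 400 at 29.8 × log2(400/30) = 111.4 days, a gap of about 75 days. If the nadir falls on a visit, 4-weekly sampling first shows these crossings at days 56 and 112, so the observed gap is 56 days before confirmation. At 85.69 days the crossings are at about 105 and 320 days. Therapy and follow-up run to at most 12 × 28 + 30 = 366 days, before visit windows. With a nadir at day 56, for illustration, the crossing of 400 would fall near day 56 + 320 = 376, after follow-up ends.

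**Step 5: cohort 1.** None of the four women had a decrease in CA-125 (2.1 and 9.2). For them r = 0, the pre-treatment value is the lowest, and the two rules coincide.

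**The case against.** The strongest reply is that 7.2 and 3.1.3 serve different purposes. One defines progression on treatment in women already in marker relapse; the other defines entry after front-line therapy. The on-study rule is also used consistently in 1.5 and 7.2. That stands: this is a design choice with a consequence, not an internal contradiction.

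Three stronger readings are tempting, and the documents do not support them.
- A reader might infer that a responder can have no PFS event of any kind before a fourfold rise. Symptoms and radiographic disease count equally under 7.2, imaging is scheduled every 3 cycles, and a new lesion is PD in 7.1.1 whatever the CA-125. The days above are therefore delays on the CA-125 route only.
- A reader might infer that the PD entry in 7.1.1 must follow the 7.2 rule. Section 7.1.1 rests on GCIG criteria and cites a reference whose title covers progression as well as response. The entry may come from there, so all that can be said is that the protocol does not state it.
- A reader might infer that planned PFS comparisons by response or dose are biased. No such comparison is planned.

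Reach is also small. PFS is exploratory, there were no responders among the first four women, and only four more are to be enrolled. The point matters only if CA-125 falls in one of them, rises again, and would give the first sign of progression.

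**Conclusion.** The point holds as a minor one. On the CA-125 route, a responder needs at least a fourfold rise from nadir, and the protocol's own relapse rule would be met at least one doubling time earlier. The size, 29.8 to 85.7 days at the minimum, rests on exponential rise at mean doubling times from four women and scales in proportion to the doubling time. Four-weekly sampling shifts the observed gap, and an earlier symptomatic or radiographic event shortens or removes it. Smaller falls are affected to a lesser degree. The response rate, the doubling-time endpoint and all cohort 1 results are unaffected. It is still worth settling before cohort 2 is analysed: the effect runs in one direction only, and it can arise only in women whose marker falls.

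**What to change.** For the PFS analysis only, define the CA-125 event by the 3.1.3 rule applied on study: a confirmed value above twice the ULN if CA-125 normalised on study, otherwise a confirmed value above twice the lowest value from the pre-treatment sample onward. Keep symptoms and radiographic disease as events. State in 9.5 that this is the PFS event, and state in 7.1.1 which definition the PD entry uses.

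The cost is a change of wording and a slightly shorter PFS for responders. Scheduled CA-125 values suffice if confirmation means two successive measurements, as in 3.1.3. Cohort 1 results do not change.

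The analysis definition should be kept separate from treatment decisions. The off-therapy criterion in 1.5 and the treatment-continuation sentence in 7.2 use the pre-treatment anchor, and the sponsor must reconcile them with 3.1.3 and 7.1.1. No treatment or stopping rule is proposed here.

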8. DATA REPORTING / REGULATORY REQUIREMENTS

Adverse event lists, guidelines, and instructions for AE reporting can be found in Section 7.0 (Adverse Events: List and Reporting Requirements).

8.1 Data Reporting

8.1.1 Method

The Office of Data Quality (ODQ) will collect, manage, and perform quality checks on the data for this study.

Version Date: 12/21/22

8.1.2 Responsibility for Data Submission

Investigative sites within DF/HCC or DF/PCC are responsible for submitting data and/or data forms to the Office of Data Quality (ODQ) in accordance with DF/HCC policies.

8.2 Data Safety Monitoring

Each participating site will conduct local data and safety monitoring in accordance with the enrolling institution's data safety monitoring plan and policies. A summary DSMC report from each site should be provided to the Study PI whenever it is generated.

The DF/HCC Data and Safety Monitoring Committee (DSMC) will review and monitor toxicity and accrual data from this study. The committee is composed of medical oncologists, research nurses, pharmacists and biostatisticians with direct experience in cancer clinical research. Information that raises any questions about participant safety will be addressed with the Overall PI and study team.

The DSMC will review each protocol up to four times a year with the frequency determined by the outcome of previous reviews. Information to be provided to the committee may include: up-to-date participant accrual; current dose level information; DLT information; all grade 2 or higher unexpected adverse events that have been reported; summary of all deaths occurring within 30 days of intervention for Phase I or II protocols; for gene therapy protocols, summary of all deaths while being treated and during active follow-up; any response information; audit results, and a summary provided by the study team. Other information (e.g. scans, laboratory values) will be provided upon request.

9. STATISTICAL CONSIDERATIONS

The primary objective is to determine the rate of antineoplastic response to zafirlukast as measured by response in CA-125 concentration.

9.1 Study Design/Endpoints

Primary Endpoint: Response rate in CA-125 per GCIG criteria.

Study Design: Two dose level pilot study.

Accrual: 8 participants

9.2 Sample Size, Accrual Rate and Study Duration

Version Date: 12/21/22

In the 4 women treated with zafirlukast 40 mg twice daily, there were no responses in terms of decline of CA-125. However, However, the mean change in CA-125 was 0.036 U/mL per day prior to treatment compared with 0.015 U/mL per day following zafirlukast (paired t-test p=0.026). This equated to a mean CA-125 doubling time of 29.8 days in the weeks prior to treatment compared with a mean doubling time of 85.69 days following treatment.

A second cohort of 4 women at 80 mg twice daily will be enrolled to assess whether CA-125 doubling time is significantly prolonged compared with pre-treatment values and whether we observe PDI inhibitory activity in plasma using Di-eosin-GSSG assay.

9.3 Analysis of Primary Endpoints

CA-125 response rate will be calculated as a proportion along with a two-stage 95% confidence interval using the Atkinson and Brown procedure.

9.4 Analysis of Key Secondary Endpoint

Calculation of CA-125 doubling time before and after initiation of zafirlukast will be performed.

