1.2 Key Secondary Objective

Assess changes in CA-125 doubling time in the 3 months prior to enrollment and following initiation of zafirlukast

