9.5 Analysis of Exploratory Objectives

- Changes PDI and ERp57 inhibitory activity in plasma, platelet-dependent thrombin will be performed by paired t-test analyses comparing baseline with C2D1 samples.
- Determine progression free survival (PFS)
- Assess the incidence of venous thromboembolism
- Assess incidence of major hemorrhage and clinically relevant non-major bleeding

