9.6 Reporting and Exclusions

9.6.1 Evaluation of Toxicity

All participants who received a dose of study drug will be assessed for toxicity.

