9.6.2 Evaluation of the Primary Efficacy Endpoint

All participants included in the study must be assessed for response to treatment, even if there are major protocol treatment deviations or if they are ineligible.

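### Do Sections 9.4 and 9.5 leave room to pool the known 40 mg result into the 80 mg before/after question?

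*Combined protocol and SAP*

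**What the plan says.** The key secondary objective in Section 1.2 makes no mention of dose: "Assess changes in CA-125 doubling time in the 3 months prior to enrollment and following initiation of zafirlukast". Section 9.1 describes a pilot with two dose levels and gives "Accrual: 8 participants". Section 9.4 is one sentence, "Calculation of CA-125 doubling time before and after initiation of zafirlukast will be performed", with no cohort, test or significance level. Section 9.5 says that changes in PDI and ERp57 inhibitory activity and platelet-dependent thrombin "will be performed by paired t-test analyses comparing baseline with C2D1 samples", again with no cohort.

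Section 9.2 is more specific. It gives the cohort 1 result on its own, "0.036 U/mL per day prior to treatment compared with 0.015 U/mL per day following zafirlukast (paired t-test p=0.026", for the four women at 40 mg twice daily. It then says that a second cohort of four at 80 mg twice daily "will be enrolled to assess whether CA-125 doubling time is significantly prolonged compared with pre-treatment values", and in the same sentence asks whether PDI inhibition is seen in plasma.

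Two populations are named elsewhere in Section 9. Section 9.6.1 has "All participants who received a dose of study drug will be assessed for toxicity". Section 9.6.2, on the primary efficacy endpoint, has "All participants included in the study must be assessed for response to treatment".

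**The concern.** Read alone, Sections 9.4 and 9.5 would allow a before/after test on the four women at 80 mg or on all eight. The choice matters because cohort 1 is not blank data. Its CA-125 result is known, favourable and printed in the plan. A pooled test would take half its observations from that fixed result, so a significant prolongation could be reported even if the 80 mg cohort showed almost none. That would not answer the question for which Section 9.2 enrols the second cohort. Leaving the analysis set open until cohort 2 is seen is also the kind of freedom an analysis plan normally removes.

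**Working it through.** **Inputs.** From Section 9.2: mean CA-125 change per day 0.036 before and 0.015 after, n=4, paired t-test p=0.026; second cohort n=4. Not stated, so assumed: a two-sided 5% level, normal changes, and a test on the rate scale (the scale of the reported p-value).

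**Step 1: recover the cohort 1 SD.** The p-value cannot be reproduced because no SD or individual values are given, so it is inverted. Mean change = 0.036 − 0.015 = 0.021 per day. With 3 df:
- p two-sided: t = 4.115, SD = 0.021 × √4 / 4.115 = 0.0102.
- p one-sided: t = 3.132, SD = 0.021 × √4 / 3.132 = 0.0134.

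**Step 2: the pooled statistic.** With cohort 1 fixed and an 80 mg cohort with mean change m₂ and SD s₂:
- mean = (0.021 + m₂)/2
- SS = 3·SD₁² + 3·s₂² + 2·(0.021 − m₂)²
- t = mean / √(SS/7/8), critical value 2.365 on 7 df.

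**Step 3: no true effect at 80 mg.** Four values were drawn from a normal distribution with mean 0, 400,000 draws per scenario. Chance of p<0.05 towards slowing:

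| 80 mg SD ÷ cohort 1 SD | Pooled, p=0.026 two-sided | Pooled, p=0.026 one-sided | 80 mg alone |
|---|---|---|---|
| 0.5 | 36.6% | 24.2% | 2.5% |
| 1 | 34.5% | 26.5% | 2.5% |
| 2 | 27.4% | 21.5% | 2.5% |
| 3 | 22.1% | 17.1% | 2.5% |

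**Step 4: how little 80 mg effect a pooled test would need.** Take the two-sided reading, s₂ = 0.0102 and m₂ = 0.0021. The mean is 0.01155 and SS = 6 × 0.0102² + 2 × 0.0189² = 0.00134, so t ≈ 2.36, which is the threshold. The 80 mg cohort alone would have t = 0.0021/(0.0102/2) = 0.41, p = 0.71. On the one-sided reading the threshold is 0.0045 per day, with p = 0.55 in the 80 mg cohort alone.

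These pooling percentages depend only on the cohort 1 t-value and the SD ratio, so the unclear unit of the reported rates does not affect them. No such figure can be given for PDI, ERp57 or thrombin generation, because the text gives no cohort 1 values for them.

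**Step 5: does any passage call for pooling?**
- Section 9.2 asks both questions (doubling time and PDI inhibition) of the second cohort of four, against its own pre-treatment values.
- Sections 2.1 and 9.2 both report cohort 1 by itself, so the study's practice so far is by cohort.
- Section 9.6.1 governs toxicity and Section 9.6.2 governs CA-125 response. Neither sets a population for doubling time or PDI.
- The accrual of 8 in Section 9.1 is 4 + 4, a headcount.
- No sentence says that the cohorts will be combined for a before/after test.

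**The case for a change.** The strongest case for a change is that Section 9.2 states a purpose and does not define an analysis set. The sections meant to carry out that purpose are silent, so a test on eight would not breach the plan. Every scenario tried for a zero 80 mg effect shows at least a sixfold inflation (17.1% against 2.5%), and a line of text would close the gap.

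The silence and the arithmetic both stand. Two things limit their weight. First, the 34.5% is not the false-positive rate of a pooled test for its own question. It fixes 40 mg at its observed effect and sets 80 mg to zero. A pooled test asks whether zafirlukast at either dose slows CA-125, and if 40 mg does, rejection is not an error for that question. It becomes misleading only if presented as the answer to the 80 mg question, and Section 9.2 frames that question for the second cohort. Second, the zero-effect scenario is at odds with the plan's own premises: Section 2.1 suggests that higher doses may inhibit PDI further, and Section 4.1.1 describes roughly linear pharmacokinetics from 5 mg to 80 mg.

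A fuller rewrite, with a log-slope estimator, a fixed post-treatment window and a minimum number of values per window, would go beyond the cohort question. It has not been shown to correct a wrong result.

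**Conclusion.** The concern does not call for a change. Sections 9.4 and 9.5 omit the cohort, but Section 9.2 states it for both endpoints, and cohort 1 has been reported alone throughout. An analyst would fill the gap by testing the 80 mg women against their own pre-treatment values. In this pilot of eight, Section 9.4 itself promises only a calculation.

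Pooling would matter if it were done and presented as the 80 mg answer. At equal SDs and no 80 mg effect, significant slowing would appear in about 26% to 35% of trials, depending on whether p=0.026 is one- or two-sided, against 2.5% for the 80 mg cohort alone. Over SD ratios from 0.5 to 3 the pooled range is about 17% to 37%. These figures assume normal changes, a two-sided 5% test on the rate scale, and cohort 1 held at its reported values. They describe an analysis that the documents do not plan.
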